## **1. INTRODUCTION**

### **1.1. Background**

Noribogaine is being developed as a treatment for alcohol use disorder based on accumulated knowledge of the pharmacology and toxicology of noribogaine which has been shown to have efficacy in animal models of alcohol addiction .

Alcohol addiction encompasses the dysregulation of multiple central nervous system pathways involved in executive function leading to excessive consumption of alcohol, despite negative health and social consequences, and withdrawal symptoms when access to alcohol is prevented . Ethanol exerts its toxicity through changes to multiple neurotransmitter systems, including serotonin, dopamine, gamma-aminobutyric acid, glutamate, acetylcholine, and opioid systems. These neurotransmitter imbalances result in dysregulation of brain circuits responsible for reward, motivation, decision making, affect, and the stress response.

Previous clinical trials have tested single and multiple doses of noribogaine in healthy individuals and opioid-dependent patients. In healthy subjects (Study ZPS-468, ACTRN1261000821897), doses from 3 to 60 mg were well tolerated with minor adverse events such as headaches and nosebleeds. Opioid-dependent patients (Studies ZPS-513, ACTRN12613001064796; DMX-100, UTN U1111-1159-4757) received higher doses (60 - 180 mg) and reported adverse events including nausea, headache, and anxiety. These could be related to opioid withdrawal or noribogaine itself. Importantly, no serious adverse reactions were observed in any trial.

Single oral administration of noribogaine shows that the drug reaches peak levels in the bloodstream within 2 - 4 hours depending on the dose, with a half-life of 24 - 50 hours. The dose and its effect on blood levels increased proportionally in healthy subjects (Studies ZPS-468). An increase in the QT interval on electrocardiograms was observed in all studies, which warrants further investigation, especially considering the presence of opioids in some studies.

Overall, these trials suggest that noribogaine can be safely administered orally at various doses and has the potential for long-acting effects in addiction treatment.

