AE = adverse event; BMI = body mass index; C-SSRS = Columbia-Suicide Severity Rating Scale; ECG = electrocardiogram; FSH = Follicle Stimulating Hormone; HCG = Human Chorionic Gonadotrophin; HIV = Human Immunodeficiency Virus, IMP = investigational medicinal product; MEQ30 = Mystical Experience Questionnaire; PK = pharmacokinetic.

a Written consent prior to the Screening window is permitted.

b Update only.

- c FSH testing is required for post-menopausal women only.
- d Serum β-HCG testing is required for women of childbearing potential (WOCBP) only.
- e Participants will be administered noribogaine or placebo capsules at H0 and H12 from D1 to D7 with a final dose on D8 at H0.
- f Participants will fast for at least 8 hours before the morning dose until at least 4 hours after dosing on all days. Participants will fast for 3 hours before the evening dose until 2 hours after dosing on all days except for Day 1 where they will fast for 3 hours after dosing. Planned D1 meal times will be followed on D-1. For all other doses participants will fast for at least 2 hours before the dose until at least 3 hours after the dose. For non-dosing days, meals will be provided at standard unit times. See [Table 3](#) for scheduled meal timepoints. Participants will refrain from consuming water from 1 hour pre-dose until 1 hour post-dose. Chilled water is not permitted on Days -1, 1 and 8 due to interference with intensive cardiac assessments.
- g Respiratory Rate, Oxygen Saturation, Tympanic Temperature, Blood Pressure and Heart Rate. Participants will be supine for a minimum of 5 minutes prior to measurements. See [Table 3](#) for Treatment Period timepoints.
- h Participants will be supine for a minimum of 10 minutes prior to measurements. See [Table 3](#) for Treatment Period timepoints.
- i 24-hour Holter ECG performed at Screening . Telemetry will be performed from at least H-24 on D-1 to H16 on D8.
- j Samples to be obtained at H0.
- k Procedure to be performed at H6.
- l See [Table 3](#) for Treatment Period timepoints.
- m Pooled urine collection will be performed H0 - 6, 6 - 12 and 12 - 24 hours post first dose on Day 1, and at H0 - 6, 6 - 12, 12 - 24, 24 - 36, 36 - 48, and 48 - 72 post last dose on Days 8 - 10. Predose sampling is to be performed within 30 minutes prior to dosing.

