2.2 Endpoints

Primary

- Maximum plasma concentration (C_{max} : Day 1 & Day 8), time to maximum plasma concentration (T_{max} : Day 1 & Day 8), trough concentration prior to next dose (C_{12} , C_{24}), area under the curve at 12 hours and 24 hours (AUC_{0-12} hours, AUC_{0-24} hours: Day 1 & Day 8, and to infinity ($AUC_{0-\infty}$)), accumulation ratio for AUC, accumulation ratio C_{max} , terminal elimination rate constant (λ_z), half-life ($t_{1/2}$), clearance (CL/F) and volume of distribution (Vz/F), whole blood to plasma ratio (1 hour, 2 hours and 6 hours), amount excreted (Ae) (Day 1 & Day 8) and cumulative amount excreted (Cum Ae) (Day 1 & Day 8).
- QT interval corrected for heart rate using individual specific QT interval correction (QTcI) measures (Day 1 & Day 8). Concentration-QTc relationship assessed on placebo-adjusted change from baseline for QTcI ($\Delta\Delta QTcI$) (Day 1 and Day 8).

Secondary

- Adverse events will be elicited by a verbal probe (prior to any trial rating scales). Any events spontaneously reported by the participant or observed by Investigator's staff (physical examinations) will be recorded. Vital signs, clinical laboratory results and ECG abnormalities will be reported as an adverse event if considered clinically significant.

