3. TRIAL DESIGN

3.1 Overall Trial Design

This trial will be a randomised, double-blind, sequential-group, multiple-dose, placebo-controlled, dose escalation trial to characterise the pharmacokinetics (PK), pharmacodynamics (PD) and safety of noribogaine in healthy adult participants.

[figure not shown]
60 healthy participants will be enrolled and randomised to receive either noribogaine or placebo.

The trial will be conducted at a single site in the UK.

The trial consists of a Screening Period (up to 35 days before Admission), followed by an Inpatient Treatment Period. Participants will stay at the trial site for 13 days and will be discharged following completion of the discharge procedures at the end of the period. Participants will return to the trial site 2 to 6 days after Discharge for the follow-up procedures (Follow-up Period).

The overall trial design is depicted in Figure 1.

Figure 1: Study flow chart

Cohorts

Eligible participants will be assigned to one of the four possible cohorts. Each participant will be randomised to receive either noribogaine capsules or placebo orally twice daily for 8 days (except Day 8, morning dose only). Each cohort will consist of 15 participants (12 will be randomised to noribogaine and 3 will be randomised to placebo). The cohorts will be administered the following doses in a sequential fashion as shown in Table 1.

Statistical Analysis Plan

Table 1. Planned Treatment Cohorts and Investigational Medicinal Product (IMP) Administration

Cohort	Number of Participants	Treatment	Planned Dose	Number of Doses
1	12	Noribogaine	1 x 10 mg noribogaine capsule	Study treatments will be administered twice daily to each participant with 240 ml of water.
	3	Placebo	1 x placebo capsule	
2	12	Noribogaine	1 x 20 mg noribogaine capsule	The treatment will be administered for 8 days (with the last dose given on morning of Day 8).
	3	Placebo	1 x placebo capsule	
3	12	Noribogaine	1 x 10 mg and 1 x 20 mg noribogaine capsules	The doses will be administered at approximately 12-hour intervals.
	3	Placebo	2 x placebo capsules	
4	12	Noribogaine	2 x 20 mg noribogaine capsules	
	3	Placebo	2 x placebo capsules	

Four cohorts of 12 participants will be enrolled, with a minimum data requirement of 8 participants dosed in order to conduct the safety review. On completion of the 4 cohorts, the remaining 3 participants from each cohort will be completed as a final group to achieve 4 cohorts of 15, as detailed above.

Periods

Screening

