4.13 Pharmacokinetic Data

Non-compartmental analysis will be used for estimation of pharmacokinetic parameters.

The following pharmacokinetic parameters will be calculated for noribogaine:

Table 5: Evaluation of Pharmacokinetic Parameters

C_{\max}	Maximal plasma concentration (Day 1 and Day 8)
t_{\max}	Time at which the maximum plasma concentration occurs (Day 1 and Day 8)
C_{12}, C_{24}	Trough concentration prior to next dose
AUC_{0-12}	Area under the plasma concentration curve from time zero to 12 hours (Day 1 and Day 8)
AUC_{0-24}	Area under the plasma concentration curve from time zero to 24 hours (Day 1 and Day 8)
AUC_{last}	Area under the plasma concentration curve to the last measurable concentration
$AUC_{0-\infty}$	Area under the plasma concentration-time curve from time 0 extrapolated to infinite time (Day 1 and 8)
$\%AUC_{\text{extrap}}$	Percentage of AUC that is due to extrapolation from t_{last} to infinity $((AUC_{0-\infty} - AUC_{0-t_{\text{last}}})/AUC_{0-\infty}) \times 100$ (Day 1 and 8)
ARC_{\max}	Accumulation ratio based on C_{\max} after the first and the last dose (C_{\max} Day 8/ C_{\max} Day 1)
$ARAUC_{\tau}$	Accumulation ratio based on $AUC_{0-\tau}$ (AUC_{τ} Day 8/ AUC_{0-12} or $0-24$ on Day 1)
$ARC_{\text{trough}2},$ $ARC_{\text{trough}3},$ $ARC_{\text{trough}4},$ $ARC_{\text{trough}5},$ $ARC_{\text{trough}6},$ $ARC_{\text{trough}7},$	Accumulation ratio based on C_{trough} on days 2-7 (C_{trough} on multiple dose day/ C_{trough} on single dose day)

Statistical Analysis Plan

λ_z	Terminal elimination rate constant obtained from linear regression of time vs log-concentration during the terminal elimination phase; using at least three time-points during the terminal elimination phase (Day 1 and Day 8)
$t_{1/2}$	Terminal elimination half-life (Day 1 and Day 8)
CL/F	Plasma clearance after extravascular administration calculated as Dose/AUC _{tau} (Day 8)
Vz/F	Apparent Volume of distribution after extravascular administration; calculated as Dose/(\mathbf{\lambda}_z * AUC _{0-inf})(Day 1, EDay 8)
Ae	Amount excreted in the urine during dosing interval (mass units)
Cum Ae	Cumulative amount excreted (mass units)
Fe	Fraction of dose excreted in urine over the collection interval; calculated as (cumulative Ae/dose)*100 (%)
Clr	Renal Clearance; calculate as Cum Ae/AUC (over equivalent interval)

Dose normalised PK parameters will be calculated as follows:

Dose normalised C_{max} = C_{max} /Dose

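### Day 8 Vz/F divides one dose by an AUC0-∞ that contains carry-over from 14 earlier doses, so it comes out about 3.4 to 6.0 times too low and contradicts CL/F in the same table

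*SAP*

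**What the plan says.** SAP section 2.2 lists "clearance (CL/F) and volume of distribution (Vz/F" among the primary endpoints, without naming a day. The Protocol's table of objectives and endpoints does the same.

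SAP section 4.13, Table 5, then gives the formulas:

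- **Vz/F:** "Apparent Volume of distribution after extravascular administration; calculated as Dose" divided by λz × AUC0-∞. The row is labelled Day 1 and Day 8, with a stray letter printed before the second day.
- **AUC0-∞:** "Area under the plasma concentration-time curve from time 0 extrapolated to infinite time (Day 1 and 8". No correction for residual drug is described.
- **CL/F:** "Plasma clearance after extravascular administration calculated as Dose/AUC" over the dosing interval (AUCtau), on Day 8.

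Footnote e to the Protocol's Schedule of Assessments has two doses a day "from D1 to D7 with a final dose on D8 at H0". SAP Table 1 says "The doses will be administered at approximately 12-hour intervals". Protocol section 1.1 reports that a single oral dose peaks "within 2 - 4 hours depending on the dose, with a half-life of 24 - 50 hours".

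**The concern.** Dose/(λz × AUC0-∞) gives Vz/F only when the AUC comes from that dose alone. On Day 8 the concentration at time zero is already high from earlier dosing, and the curve from H0 to infinity includes the elimination of all that drug. Dividing one dose by this area understates the volume.

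The table also contradicts itself. CL/F must equal λz × Vz/F. On Day 8 the CL/F row uses the multiple-dose form and the Vz/F row the single-dose form, so the two differ by the ratio AUC0-∞/AUC0-12 whatever the true volume is. A reader of the PK report would see a primary parameter several times too low beside a CL/F that does not fit it.

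**Working it through.** The documents give no value for Vz/F, so there is no figure of theirs to reproduce. The check uses superposition.

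**Inputs from the documents.** Doses up to Day 8 H0: 7 × 2 + 1 = 15. τ = 12 h. Half-life 24 to 50 h and Tmax 2 to 4 h (Protocol 1.1). Day 8 plasma times from 0 to 168 h (Schedule of Assessments). Linearity is supported by Protocol 1.1: "The dose and its effect on blood levels increased proportionally in healthy subjects".

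**Assumptions.** Linear one-compartment kinetics. Dose is the single administration. No missed doses. 36 h is taken as a middle half-life.

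**Closed form.** Let r = exp(−ln2 × 12/t½).

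- Day 8 AUC0-∞ relative to a single-dose AUC0-∞: S = (1 − r^15)/(1 − r). Planned Day 8 Vz/F is the true value divided by S.
- Share of Day 8 AUC0-∞ that is carry-over: 1 − 1/S.
- Day 8 AUC0-12 relative to a single-dose AUC0-∞: 1 − r^15.
- CL/F row divided by λz × Vz/F (should be 1): AUC0-∞/AUC0-12 = 1/(1 − r).

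| t½ | r | r^15 | S | Planned Vz/F ÷ true | Carry-over | CL/F ÷ (λz × Vz/F) | Vz/F from AUC0-12 ÷ true |
|---|---|---|---|---|---|---|---|
| 24 h | 0.707 | 0.0055 | 3.40 | 0.29 | 71% | 3.41 | 1.01 |
| 36 h | 0.794 | 0.0313 | 4.70 | 0.21 | 79% | 4.85 | 1.03 |
| 50 h | 0.847 | 0.0825 | 5.99 | 0.17 | 83% | 6.52 | 1.09 |

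**With absorption and the scheduled sampling.** The analysis was simulated on the Day 8 times with the SAP's trapezoidal rule and first-order absorption set to Tmax 2 h and 4 h. Vz/F is 3.42 and 3.48 times too low at 24 h, and 6.01 and 6.05 times at 50 h. The mismatch with CL/F is 3.46 and 3.50 at 24 h, and 6.57 and 6.61 at 50 h.

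**Two-phase kinetics.** Suppose the terminal phase holds a share w of the single-dose AUC and the fast phase has a 3 h half-life (both assumed). For the fast phase r = 0.0625 and S = 1.07. Then S = w × S(terminal) + (1 − w) × 1.07. For w = 0.5, 0.7 and 0.9 this gives 2.23, 2.70 and 3.16 at 24 h, and 3.53, 4.51 and 5.49 at 50 h. The factor is smaller but the direction is the same.

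**Does the plan's own check catch it?** Section 4.13 flags an extrapolated share above 20%. On Day 8, with the 168 h sample, the share is about 0.8% at 24 h and 9.8% at 50 h, so the biased value passes. On Day 1, where the formula is valid, only 12 h of data precede the next dose. The share is 72 to 86%, so that value is flagged and may be excluded.

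**Accumulation ratio in the same table.** The AUC ratio leaves τ undefined and allows either a 12 h or a 24 h window on Day 1. Over the same half-life and Tmax range, 0-12 over 0-12 gives 3.5 to 6.5. A 0-24 over 0-24 ratio gives 2.2 to 4.1, and sets two doses on Day 1 against one on Day 8. Day 8 0-12 over Day 1 0-24 gives 1.3 to 2.2.

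**The case against.** The strongest objections concern scope rather than arithmetic.

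- **Day label.** The stray letter leaves some doubt about the row's label, and the endpoint list names no day for Vz/F. However, Table 5 assigns both λz and AUC0-∞ to Day 8, so Day 8 is the natural reading. If it was not meant, the row still needs correcting.
- **Meaning of Dose.** Table 5 does not define it. If the daily dose were meant, the understatement would be half as large: 1.7 to 3.0 times. SAP Table 1 lists the dose per administration, which favours the larger figures.
- **Standard equations.** Section 4.13 falls back on standard equations, but only for parameters other than those already given a rule. Vz/F has an explicit formula.
- **Extrapolation check.** The 168 h sample might not be measurable; no quantification limit is given. If the last usable sample were at 72 h, the Day 8 share would be 13%, 25% and 37% at 24, 36 and 50 h. The longer half-lives would then be flagged, but for extrapolation and not for carry-over.
- **Consequence.** Vz/F is descriptive, enters neither the dose-proportionality nor the concentration-QTc model, and can be recomputed from the listed λz and AUC0-12. This stands and limits the importance of the point.
- **CL/F is not exact either.** At a 50 h half-life it is about 9% high, because Day 8 is not fully at steady state. This also stands.

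**Conclusion.** The concern holds. As written, the SAP would report a Day 8 Vz/F about 3.4 to 6.0 times too low over half-lives of 24 to 50 h. This rests on linear one-compartment kinetics and Dose as the single administration. Under the two-phase check the range is 2.2 to 5.5 times. The direction is the same in every case examined, and the conflict with the CL/F row does not depend on the true volume. The error affects the reported level of a named primary PK parameter, not the QTc conclusion or, under linear kinetics, the dose-proportionality slope. It should be fixed before the PK analysis is run.

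**What to change.** In Table 5, define Day 8 Vz/F = Dose/(λz × AUC0-12 on Day 8), state that Dose is the single administration and τ = 12 h, and correct the day label. Add a footnote that Day 8 CL/F and Vz/F run about 1% high at a 24 h half-life and 9% at 50 h because steady state is incomplete.

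Smaller clarifications to make in the same edit:

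- Define the AUC accumulation ratio as AUC0-12 on Day 8 over AUC0-12 on Day 1, and drop the 24 h alternative. Report Day 8 AUC0-24 as descriptive after one dose.
- Remove CL/F from the list of λz-dependent parameters in section 4.13, since it is calculated from AUCtau. Keep Vz/F there.
- Label Day 8 AUC0-∞ and its dose-normalised value as including carry-over, and name the day used in section 4.13.2.
- State the day and dose basis of Fe. One Day 8 dose set against urine over 0-72 h would give 3.0 to 3.8 times the true fraction; over 0-12 h it gives 0.92 to 0.99.
- Optionally, stop reporting the Day 1 terminal parameters, which would be flagged anyway. Because AUC0-∞ is in the Protocol's primary endpoint list, check first whether that list requires it on Day 1.

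The Vz/F correction needs SAP wording only: no new samples and no change to the design.

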4.13.1 Statistical Analysis on PK Parameters

PK analyses from blood samples will be performed on the PK set.

Plasma concentrations, including whole blood to plasma concentration ratios, will be listed and summarised by time point (N - the number of participants, n - the number of samples, n(LLOQ) - the number of samples <LLOQ, arithmetic mean, SD - standard deviation, CV - coefficient of variation, geometric mean, median, minimum, maximum). If all the values are BLQ, then the arithmetic mean, arithmetic SD, median, minimum, and maximum will be presented as 1, and the geometric mean and geometric CV will be denoted as zero.

The PK parameters (Table 5) will be listed for each participant and summarized for each treatment group using descriptive statistics by treatment (N - the number of participants, arithmetic mean, SD - standard deviation, CV - coefficient of variation, geometric mean, median, minimum, maximum) except t_{max} . The t_{max} summary statistics will be provided as n, minimum, median, and maximum only. For the calculation of summary statistics of PK parameters, all not reported values (parameters which cannot be calculated) will be set to missing. PK parameters will be presented as given in the raw data. Descriptive statistics for PK parameters will be reported to 3 significant figures.

In addition, concentration figures over time will be presented by subject (combined in one figure by treatment) as mean (\pm SD) concentration, both on linear and logarithmic scale. Figures will be presented by treatment. BLQ values will be set to 0 on the linear scale, and LLOQ x 0.5 on the logarithmic scale.

4.13.2 Dose Linearity Analysis

Dose proportionality of noribogaine pharmacokinetics will be evaluated using a power model regression approach, as recommended by FDA and EMA guidelines. The following PK parameters will be assessed across different dose levels: C_{max} , AUC_{0-12} , AUC_{0-24} , and AUC_{0-inf} .

The log-log regression model will be applied using the following equation:

$$\log(\text{PK Parameter}) = \beta_0 + \beta_1 \log(\text{Dose}) + \epsilon$$

where β_1 (slope) represents the dose proportionality exponent. Dose proportionality will be concluded if β_1 lies within the acceptance range of 0.75–1.25 and its 90% confidence interval (CI) includes 1.

To further support the assessment, descriptive statistics for dose-normalized PK parameters (C_{max}/Dose and AUC/Dose) will be presented.

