3.2 Sample Size

The sample size was selected on the basis of the Sponsor's prior PK studies of similar size in which a dose response in QTc was observed across the expected range of doses and exposures. Using results from a simulation based on data from a prior trial in healthy volunteers, the probability is 95% that a sample size of 12 subjects will produce a two-sided 95% confidence interval with a distance from the mean to the limits that is less than or equal to 0.2 if the population standard deviation is estimated to be no more than 0.2 on the natural log scale. This corresponds to a calculated geometric mean of approximately 80 ng/mL with an upper bound of the 95% confidence interval being less than or equal to 100 ng/mL. The standard deviation is expected to be less than or equal to 20 ng/mL.

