Dose normalised AUC_{0-12} = AUC_{0-12} /Dose

Dose normalised AUC_{0-24} = AUC_{0-24} /Dose

Dose normalised AUC_{0-inf} = AUC_{0-inf} /Dose

The individual plasma concentration data, and the actual time for noribogaine administration and blood sampling will be used in the derivation of the PK parameters. If there is any doubt in the actual time a sample was taken, then the scheduled time will be used.

AUC_{0-t} and AUC_{0-inf} will be calculated using the linear trapezoidal linear/log interpolation method, applying the linear trapezoidal rule up to C_{max} and the log trapezoidal rule for the remainder of the curve. Samples below the lower limit of quantification (LLOQ) prior to the C_{max} will be set to zero. Samples with concentrations below LLOQ after C_{max} will be set to 'missing' and omitted from the analysis. Other pharmacokinetic parameters will be calculated according to standard equations.

In the determination of λ_z (and AUC_{0-inf}), the following conditions should be met:

- A minimum of at least 3 data points in the terminal elimination phase, in which C_{max} is not included;
- The Adjusted R-squared should be ≥ 0.8 , and

- %AUCextrap < 20%.

If these conditions are not met, the PK parameter will be flagged in the listings (together with those dependent on λ_z , such as $t_{1/2}$, CL/F and V_z/F) and they may be excluded from the summary statistics. The decision to include these parameters will be based on the decision of the Sponsor with input from the pharmacokineticist. The following flags/footnotes may be applied to the PK parameters:

Flag	Footnote
a	Adjusted R-squared of regression was <0.8
b	Extrapolated portion of $AUC_{0-\infty}$ >20%
c	Insufficient post- C_{max} data points for estimation of lambda-z
d	Regression line could not be fitted

If plasma concentrations are all below the limit of quantification (BLQ), then PK parameter estimation and all subsequent statistical summaries will not be possible.

Whole blood to plasma concentration ratios will be determined on Day 1 at 1 hour, 2 hours and 6 hours.

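### The dose-proportionality rule asks only that the slope's 90% CI include 1, so at a log SD of 0.2 it fails 55% of trials whose true slope is 1.10

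*SAP*

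**What the plan says.** SAP 4.13.2 (Dose Linearity Analysis) regresses the log of each PK parameter on log dose for Cmax, AUC0-12, AUC0-24 and AUC0-inf. Proportionality is concluded if the slope "lies within the acceptance range of 0.75–1.25 and its 90% confidence interval (CI) includes 1". Dose-normalised descriptive statistics are added in support but have no part in the decision. Neither document gives an error rate or power for this rule, or a basis for the range 0.75–1.25.

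The only planning variability is in SAP 3.2. It supposes that the "population standard deviation is estimated to be no more than 0.2 on the natural log scale", and adds: "The standard deviation is expected to be less than or equal to 20 ng/mL", around a geometric mean of about 80 ng/mL. The PK measure concerned is not named.

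**The concern.** The rule joins two conditions of different kinds. The range 0.75–1.25 reads as a statement of which slopes are close enough to 1, but it is applied to the estimate without regard to its precision. The CI is then asked only to include 1. That is a significance test of slope = 1 that must come out non-significant, and failing to reject does not show that the slope is near 1.

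Two errors can follow:

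- **Precise data.** A small departure, well inside the SAP's own range, excludes 1 and fails.
- **Imprecise data.** A wide interval almost always includes 1, so a slope at the edge of the range can pass.

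The rule yields a prespecified yes/no statement for each of four parameters, and Cmax and the AUCs are primary endpoints. Protocol 1.1 reports proportional exposure in an earlier healthy-volunteer study, so a failure here could look like a contradiction when it reflects only a small departure measured well.

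**Working it through.** **The plan's own figure.** SAP 3.2 says that 12 participants give a 95% probability of a 95% CI half-width of at most 0.2 at log SD 0.2. With the SD known, P(t(0.975, n−1)·s/√n ≤ 0.2) is 99.6% at n = 12, and the smallest n reaching 95% is 10 (96.0%). If the SD is instead treated as estimated from a prior sample of about 17 to 26 people (a size not in the documents), 12 is the smallest n that reaches 95%. Also 80·exp(0.2) = 97.7, below 100 ng/mL as stated. The figure is at worst conservative, and nothing below depends on it.

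**Inputs.** Doses are 20, 40, 60 and 80 mg per day (protocol synopsis), with 12 active participants each (SAP 3.1). Placebo does not enter the model. The log SD is 0.2, or √ln(1 + (20/80)²) = 0.246 from the ng/mL figures. Residual df = 48 − 2 = 46 and t(0.95, 46) = 1.679.

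**Slope precision.** The ln(dose) values are 2.996, 3.689, 4.094 and 4.382, with mean 3.790. The squared deviations sum to 1.084, so Sxx = 12 × 1.084 = 13.01 and √Sxx = 3.607.

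- SD 0.2: SE = 0.2/3.607 = 0.0554; 90% CI half-width h = 1.679 × 0.0554 = 0.093.
- SD 0.246: SE = 0.0683; h = 0.115.

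**The two rules side by side.** The plan passes if |b − 1| ≤ h and |b − 1| ≤ 0.25. A rule that puts the whole CI inside 0.75–1.25 passes if |b − 1| ≤ 0.25 − h. The plan's limit therefore widens as precision worsens, while the other narrows. They meet at h = 0.125, which is an SD of 0.125 × 3.607/1.679 = 0.27.

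Example at SD 0.2: b = 1.12 has CI 1.12 ± 0.093 = 1.03 to 1.21. All of it lies inside 0.75–1.25, yet it fails because it excludes 1.

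**Probability of concluding proportionality** (1,000,000 simulated trials per cell; plan / whole CI within range):

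| True slope | SD 0.2 | SD 0.246 |
|---|---|---|
| 1.00 | 90% / 99.5% | 90% / 95% |
| 1.05 | 77% / 97% | 81% / 89% |
| 1.10 | 45% / 85% | 58% / 70% |
| 1.15 | 15% / 55% | 30% / 42% |
| 1.25 | 0.3% / 5.0% | 2.5% / 5.0% |

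At SD 0.2 and slope 1.10, the noncentral t gives a 55.3% chance that the CI excludes 1. The point estimate leaves 0.75–1.25 in only 0.3% of trials, so the CI condition drives the failures. In 40% of trials the whole CI is inside the range and the plan still fails.

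**Dependence on precision, slope 1.10.** The plan fails 97% of trials at SD 0.10, 77% at 0.15, 55% at 0.20, 32% at 0.30 and 23% at 0.40.

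**The other direction (assumed conditions, not in the documents).** At true slope 1.25 the plan passes 9% at SD 0.3 and 28% at SD 0.4, against 5% for the whole-CI rule. With only 6 evaluable per dose it passes 7% at SD 0.2 and 19% at SD 0.246, again against 5%.

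**The case against.** Several points on the other side have weight.

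- **The headline depends on assumptions.** The 0.2 is a ceiling for an unnamed measure. Using it as the residual SD of Cmax and each AUC is an assumption, and slope 1.10 is an illustrative choice. At 0.246 the failure rate is 42%, and the gap between the rules shrinks from 40 points to 12. This stands. But because 0.2 is an upper limit, a smaller SD is also in scope, and it makes the failures more frequent.
- **Escalation may stop early.** The protocol speaks of four possible cohorts. With three (20, 40 and 60 mg per day, 12 each), SD 0.2 and slope 1.10, the rules are nearly equal: 62% for the plan, 64% for the whole-CI rule. At SD 0.246 the plan passes more often, 71% against 48%. The arithmetic is right, but in that last case the plan also accepts a slope of 1.25 in 14% of trials against 5%. This is the same fault in the other direction.
- **The change loosens the rule at the planned SD.** At slope 1.15, which is 4^0.15 = 1.23 or 23% higher dose-normalised exposure across the range, acceptance rises from 15% to 55%. A strict rule can be defended, but it should be strict by choosing a narrower range, not by an accident of sample size and variability. The SAP needs to justify its range under either rule.
- **The SAP does not say that failing means not proportional.** True. It leaves the meaning of failure open, which is itself worth settling.
- **Loss of evaluable participants.** SAP 4.13 says of flagged parameters that depend on λz that "they may be excluded from the summary statistics". It does not say they leave the power model, and Cmax, AUC0-12 and AUC0-24 do not depend on λz. The case of 6 per dose is therefore only a sensitivity check.
- **Little depends on the result.** Escalation review and the concentration-QTc model do not use it, and dose-normalised summaries are planned anyway. This limits the importance of the point but does not make the rule sound.

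**Conclusion.** The concern holds: the rule is wrong as written and should be fixed. It tests for no detectable departure from slope 1 while appearing to test for closeness to 1.

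At the planned variability, with four full cohorts, the harm is failure to conclude proportionality when kinetics are nearly proportional. At a true slope of 1.10 this happens in 55% of trials at log SD 0.2 and 42% at 0.246, against 15% and 30% under a whole-CI rule. False acceptance is not the problem at those SDs, where the plan is the stricter rule at the 1.25 limit. It becomes one above a log SD of about 0.27, or with clearly fewer evaluable participants or dose levels.

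The figures assume that the SAP 3.2 variability applies to each PK parameter. The effect is confined to a supportive PK conclusion and does not touch the primary concentration-QTc analysis or participant safety.

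**What to change.** Replace the decision sentence in SAP 4.13.2 with: *Dose proportionality will be concluded for a parameter if the entire 90% CI for the slope lies within 0.75–1.25; otherwise it will be reported as not demonstrated. The slope and its 90% CI will be reported in either case.* Delete the requirement that the CI include 1.

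Add a line giving the basis for 0.75–1.25. Over this 4-fold dose range a slope of 1.10 means 4^0.10 = 1.15, or 15% higher dose-normalised exposure at the top dose than at the lowest, and 1.25 means 4^0.25 = 1.41, or 41% higher. If that is too much, narrow the range.

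No new data or participants are needed. Statistically, acceptance of a slope exactly at 1.25 rises to the nominal 5% (from 0.3% at SD 0.2). If variability is well above plan, a truly proportional drug will more often be reported as not demonstrated: the whole-CI rule succeeds at slope 1.00 in 81% of trials at an assumed SD of 0.3, 44% at 0.4 and 1% at 0.6. For data that imprecise, not demonstrated is the accurate description.
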